**Step 9: For all participants who decide to take PrEP, the study nurse will draw blood to test for baseline creatinine tests**

- Women with low creatinine can participate in the study but can only receive PrEP if their eGFR >60mL/min
- Test results will be received in 24-48 hours. If eGFR <60mL/min then the nurses will call participant to return and immediately stop using PrEP until they have a normal creatinine result (can return in following month)

**Step 10:** Participants who opt to take PrEP will receive counselling on the risks and benefits of PrEP. Following the counseling they will be asked: “Do you want to start taking PrEP today to prevent HIV? You will need to take it daily for it to be effective.” Her response will be recorded.

If yes:

1. The nurse will provide the participant with a 1-month supply of TDF-FTC and invite her to return in 1 month for her next study visit (after then they will receive 3 months prescriptions to correspond with their quarterly PrEP-PP study visit).
2. Nurses will provide contact information to the participant and ask her to call to report any side effects or adverse events while on PrEP, and nurse will track and report serious adverse events to study PIs, Pediatrician, and Obstetrician to decide on how to treat women and infants who have adverse events.

If she says she does not want to start PrEP, woman will be in the deferred PrEP arm:

1. The nurse will schedule her to return in 3 months for the follow-up study visit

**Step 10:** Participants will receive study staff contact information, instructions to call with any questions, and will be scheduled for their next visit in 1 month if on PrEP, or 3 months if not on PrEP, for the next study visit

**Step 11:** The study counselor will provide the mother with an appointment card and invitation for her partner to return to receive couples' HIV testing and counseling (if in a relationship). The session will end by encouraging the client to implement her/his risk-reduction plan (including PrEP if applicable and consistent condom use, couples testing) to prevent HIV acquisition.

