**Step 12:** The participant will receive a snack and reimbursement for her time and transportation (up to R250 in a Shoprite voucher, refreshment and reimbursement for transportation) which is in line with our ongoing research at these sites. Further, we will combine the study visits with existing ANC or post-partum/well-baby visits to minimize the travel to the facilities outside of normal clinical checkups.

2. For follow up return visits:

Follow up visits will be at 1 month after baseline (to coincide with ANC visits) then after two months after birth then every 3 months thereafter (to coincide with post-partum, well-baby visits).

COVID update: During the COVID-19 lockdown, we will offer women the option of participating in interviews over the phone with participants who are willing and unable to attend the study visit. The interviewer will be in a private room and will ask the participant to be in a private, quiet space. The interviewer is an experienced isiXhosa -speaking research assistant and interviews will be conducted over the phone while the interviewer collects the data on the tablet using RedCap. Updated processes include:

- **Calling participants who miss study visits to assess if they wish to participate a phone interview (and schedule a time when they can be alone in a quiet place for 20-30 minutes)**

The interviewer will ascertain the participant ID and date of birth to ensure that they are speaking with the participant.

**Step 1:** In ANC: Healthcare providers provide counseling on HIV prevention and treatment at each ANC visit including HIV testing, as part of standard of care. In post-natal care and well-baby visits women may not receive regular HIV testing and messages and will receive this within step 2 (with study counselor). Following their ANC visit, enrolled women will be invited to attend the study site in each MOU to do the follow-up visit including the survey and prescription and adherence counseling (if on PrEP).

**Step 2:** Survey at each visit in a private study room

**Step 3:** In the study room, the study counselors will provide PrEP-specific counseling including adherence counseling for those on PrEP (and management of side effects), or counseling about the risks and benefits of PrEP for women not yet on PrEP. Women not on PrEP will be asked if they are interested in starting PrEP at this visit.

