#### **Laboratory tests in women on PrEP:**

- **Renal function (in all women on PrEP):** Blood draws for creatinine levels will be taken at baseline, 3-month follow-up and at the end of the study, as per SA HIV Clinician Guidelines [26].
  - At enrollment: women with eGFR<60ml/min will be excluded from the study
  - At 3-month follow up: Women will not be able to continue taking PrEP with an eGFR <60m/min but will be able to continue to participate in the study. If their creatinine results change at the following visit they will be eligible to start PrEP.
- **DBS:** Dried blood spots will be prepared from finger pricks every three months in women on PrEP to evaluate adherence.
  - DBS cards will be prepared and stored following standard protocols and stored at -80°C for analysis at the end of the study with the clinical pharmacoanalytic laboratory of [name] at UCT. Using techniques developed by [name] at University of Colorado [16] adherence will be defined as red blood cells containing TDF-DP  $\geq 40\text{ng/dl}$  which is indicative of daily dosing [16]. As supplementary measures of PrEP adherence, we will use self-reported items that we will adapt from previous studies (including visual analogue scales as well as 3-day, 30-day and last visit recall questionnaires) (22-25), and pharmacy refill records to compare objective versus subjective measures and report on the effectiveness of each measure in correlation to the true measures of TDF-DP. We will determine final dosing and measures following reporting from ongoing PK studies of pregnant women on PrEP (e.g. Impaact 2009).
- Two self-collected vaginal swabs will be taken at enrollment and at 1-month visit. These will be stored at -80°C at University of Cape Town until processing for STI testing (at 2-3 weeks) and end of study

for bacterial and viral metagenomic sequencing. Briefly this will include microbial DNA extraction and shotgun metagenomic sequencing as performed previously by the [name] Lab (Brown, BP Biorxiv 2019).

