## Adverse events:

- **Maternal adverse events:** We will collect data on maternal adverse events by asking mothers about intercurrent medical events, which will be reviewed by an obstetrician, including any hospitalizations or illnesses. We will also track and report changes in creatinine or other toxicities in women on PrEP.
- **Infant adverse events:** We will collect data on infant adverse events by asking mothers about infant health or intercurrent medical events, which will be reviewed by a pediatrician.
  - Adverse birth outcomes will include infants that were small for gestational age, pre-term births, miscarriage and stillbirths.

Table 1: PrEP-PP cohort measures by participant study month

and breastfeeding in local languages (at each visit)																
Routine ANC and postnatal care, well-baby visit follow-up (as available in standard of care), including rapid HIV testing, pregnancy, and birth outcomes	X	X	X	X	X	X	X		X		X		X			X
Survey to collect: behavioral acceptability, knowledge, and substance use data	X	X	X	X	X	X	X		X		X		X			X
Screening at enrolment for Hepatitis B and creatinine. If HBsAg+ = excluded from study; if creatinine eGFR<60, excluded from study	X															
Laboratory testing for STIs (chlamydia, gonorrhoea) & treatment if positive	X				X		X									
For women on PrEP:																
Laboratory tests of creatinine (if eGFR<60ml/min cannot continue on PrEP)	X			X												X
PrEP pharmacy refills and adherence supportive counseling monthly (for first 3 months on PrEP) then every 2 months for following months	X	X	X		X		X		X		X		X			X
Laboratory testing: renal function, hepatitis B; DBS taken for TDF-DP adherence measures (bi-monthly in participants on PrEP)	X	X	X		X		X		X		X		X			X
In-depth interviews for 30 participants per site (N=60) among 30 PrEP users and 30 non-PrEP users						X										X
Collect study data on: (1) PrEP counseling, (2) PrEP medication when requested, (3) regular appointments, (4) IEC materials, (5) adherence counselling and support by facility, through patient survey at every study visit	X	X	X	X	X	X	X	X	X	X	X	X	X	X	X	X
Vaginal swab for microbiome	X		X*													

\*between 24 and 28 weeks gestational age.

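### The protocol contradicts itself on whether an enrolment eGFR below 60 means study exclusion or no PrEP, and its creatinine schedules conflict and write no draw before a late start

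*Combined protocol and SAP*

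**What the plan says.** - **Enrolment rule.** Protocol section 5, laboratory tests in women on PrEP: "At enrollment: women with eGFR<60ml/min will be excluded from the study". Protocol Table 1, enrolment screening row: "if creatinine eGFR<60, excluded from study". Protocol section 5, enrolment visit, Step 9: "Women with low creatinine can participate in the study but can only receive PrEP if their eGFR >60mL/min". On a low result, Step 9 adds: "If eGFR <60mL/min then the nurses will call participant to return and immediately stop using PrEP". That sentence goes on to make resumption wait for a normal result and allows a return the next month.
- **Who is tested.** Step 9: "For all participants who decide to take PrEP, the study nurse will draw blood to test for baseline creatinine tests". Step 5 and the screening consent in section 7 name only HIV and hepatitis B tests. Table 1 puts creatinine next to hepatitis B in its enrolment screening row, above the block of rows for PrEP users.
- **First supply.** Step 9 expects the result in 24 to 48 hours. Step 10 asks whether the woman wants to start that day and, if so, hands over one month of drug.
- **Schedule.** Laboratory section: "Blood draws for creatinine levels will be taken at baseline, 3-month follow-up and at the end of the study". One Table 1 row matches this. Another reads "Laboratory testing: renal function, hepatitis B; DBS taken for TDF-DP adherence measures (bi-monthly in participants on PrEP".
- **Late start and restart.** Follow-up visits, Step 3: "Women not on PrEP will be asked if they are interested in starting PrEP at this visit". SAP section 1 counts initiation at any point in the study, and both documents allow stopping and re-initiation. Follow-up Step 4 draws creatinine from participants on PrEP. After a low eGFR at 3 months, the laboratory section keeps the woman in the study off PrEP and makes her eligible again if the result at her next visit has changed.

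**The concern.** Two staff members who follow different parts of section 5 would handle the same woman differently: one would remove her from the study, the other would keep her without PrEP. That affects eligibility and follow-up, and it decides who belongs to the active cohort that forms the initiation denominator.

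The schedule matters for safety. Section 1 of the protocol says PrEP is not for women with reduced renal function, and the internal monitoring section sends any laboratory value that requires stopping PrEP to the DSMB. Both depend on knowing who is drawn and when. The design invites women to start or restart after enrolment, and these are the women for whom the text does not expressly write a draw. The SAP's Table 1 also plans to compare change in creatinine clearance by PrEP use, which needs one settled schedule.

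**Working it through.** 1. **Enrolment rule.** The laboratory section and the Table 1 screening row both concern enrolment, and both exclude. Step 9 also concerns enrolment, and retains without PrEP. All three cannot hold. The 3-month rule (stop PrEP, stay in the study) concerns another time point and neither conflicts with the exclusion nor settles it. The exclusion list in section 4 covers past renal disease but sets no eGFR limit.

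2. **Who is tested.** Steps 5 to 9 lead to a creatinine draw only in women who have enrolled and chosen PrEP. The Table 1 screening row, by its position, can be read as covering every enrollee. The text does not say which applies.

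3. **Supply against result.** PrEP is conditional on eGFR above 60, but the drug can be in hand one to two days before the result, with a recall if it is low. The condition and the sequence need one consistent statement.

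4. **Schedule.** I counted the marks in the 16 columns of protocol Table 1 by position, because the month headings are not readable in the text available.
   - Creatinine row: columns 1, 4 and 16 (3 marks).
   - Renal function and DBS row: columns 1, 2, 3, 5, 7, 9, 11, 13 and 16 (9 marks).
   - Shared: columns 1 and 16. Only in the first row: column 4. Only in the second: seven columns.

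   The mismatch does not depend on the headings.

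5. **Late start and restart.**
   - *First start at a follow-up visit:* the pre-PrEP draw is described only under the enrolment visit, and the follow-up draw is for women already on PrEP. No draw is expressly written before the start.
   - *Restart after a low eGFR:* Step 9 and the laboratory section both require a new result. The three-point schedule has no draw for it.
   - *Restart after stopping for another reason:* no test is stated.

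6. **Size in the cascade.** The plan's own figures reproduce: 1200 × 0.60 = 720 initiators and 720 × 0.75 = 540 continuing. The documents give no rate of eGFR below 60, so I assume 0.5% to 3% of the 720, or 3.6 to 21.6 women.
   - Initiation if they are excluded: (720 − 3.6)/(1200 − 3.6) = 59.9%; (720 − 21.6)/(1200 − 21.6) = 59.3%; against 60.0%.
   - Initiation if they are kept but not counted as initiators: 716.4/1200 = 59.7%; 698.4/1200 = 58.2%.
   - Continuation if they are excluded and none would have continued: 540/(720 − 3.6) = 75.4%; 540/(720 − 21.6) = 77.3%; against 75.0%. If they would have continued at the same 75%, it does not move.

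**The case against.** The strongest reply is that much of this can be read coherently and that the numbers barely move. Several stronger readings are tempting, and the documents do not support them.

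- A reader might infer that PrEP can resume after a low eGFR with no test. It cannot: Step 9 and the laboratory section both require a new result. Only the scheduled draw is missing.
- A reader might infer that exclusion can reach only women who accept PrEP, leaving untested decliners in. That follows from Steps 5 to 9, but Table 1 can be read as testing everyone. The point is ambiguous, not settled.
- A reader might infer that a woman starting after month 3 goes untested until study end. The laboratory section is written for women on PrEP, so its baseline may mean the start of PrEP. Table 1 is titled by study month, but its refill row counts the first months on PrEP, and under the nine-mark row she would be tested sooner. An enrolment result, if every woman has one, could still be months old.
- A reader might call this the only renal safeguard. Section 4 also excludes past renal disease, and section 5 tracks creatinine changes on PrEP.
- The phrase about low creatinine in Step 9 is a wording slip, since the same sentence gives the eGFR threshold. A same-day start with a written recall is workable; it does not sit with the stated condition.

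On analysis, the SAP already counts a start at any time as initiation and tabulates reasons for ending treatment. It does not say what happens to a woman dispensed PrEP and then excluded. None of this removes the conflict over the enrolment rule or between the two Table 1 rows.

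**Conclusion.** The point stands as an internal inconsistency in a safety and eligibility rule, and it should be corrected. Two parts are certain from the text: the enrolment rule says both exclude and retain, and the two renal rows of Table 1 cannot both be followed. Who is tested at enrolment, and whether supply may precede the result, are also stated inconsistently. The late-start part holds in the limited sense that no draw is expressly written, not that testing is ruled out.

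The statistical effect is small: at most 0.7 percentage points on initiation and 2.3 on continuation if the women are excluded. These are upper figures for the assumed 0.5% to 3%. They apply the rate to all 720 initiators, although an enrolment exclusion reaches only those tested at enrolment, and the continuation figure assumes that none of the women would have continued. The case therefore rests on consistent handling of participants, not on bias.

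**What to change.** Reconcile protocol section 5 (enrolment Steps 5, 9 and 10, follow-up Steps 3 and 4, and the laboratory section) with the Table 1 rows, so that one statement says:

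- who has creatinine drawn at enrolment;
- whether eGFR below 60 means exclusion from the study or no PrEP;
- whether PrEP may be dispensed before the result is known;
- what the single creatinine schedule is, including how the eGFR condition is applied to late starters and to women who restart.

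The clinical rule and the schedule are the sponsor's to choose. Correct the creatinine wording in Step 9 at the same time.

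In the SAP, state that every woman dispensed PrEP counts as an initiator whatever her later eGFR result, that she stays in the continuation denominator, and that eGFR stops are reported as a separate reason.

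The cost is amendment wording and a line or two in the SAP. Whether any extra blood draws follow depends on the schedule the sponsor settles on.

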## **Laboratory tests in all women in the cohort:**

- **STI testing:** Self-collected vaginal swab kits will be provided to all participants along with an explanation for their use. Swabs will be analyzed in the laboratory for chlamydia and gonorrhea. Results for STI testing will be provided in 2-3 weeks after analysis and participants will be called in with STI+ results for treatment and partner referrals
- **HIV testing.** As part of the standard of care, all pregnant and breastfeeding women will be tested for HIV using serial rapid HIV tests at each antenatal and postnatal care visit. In addition, PrEP-PP study staff will test for HIV using antigen and antibody HIV tests to rule out acute HIV infections.
  - **Seroconversion.** If a woman, infant or partner seroconverts at any point during the study (including antigen+, antibody+ or antibody/antigen+), they will stop PrEP immediately and be referred to the clinician on duty to initiate ART on the same day, following counseling about PMTCT, breastfeeding, disclosure, and ART adherence, per the SA National Protocols [17]. Seroconverted women will be censored from the remainder of the study and referred to the clinic to initiate ART.
  - If a woman seroconverts while on PrEP, there may be a risk of ART resistance, though research has demonstrated that the risk of ART resistance is very low [12, 13]. In the case of seroconversion, Drs [name] and [name] will follow seroconverters with the study team to evaluate if the patient achieves viral suppression within 6 months of ART start, and if not, she will be referred for specialist attention for testing for ART resistance and clinical follow-up.

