### **1. Determine the distribution of women across the PrEP cascade:**

- (1) Evaluate the proportion of pregnant and breastfeeding women who initiate PrEP out of all women offered PrEP**
- (2) Evaluate the proportion of pregnant and breastfeeding women who are retained in the PrEP cohort**
- (3) Evaluate the proportion of pregnant and breastfeeding women who initiate PrEP who adhere to PrEP using objective dried blood spot measures and subjective measures of self-reported pill count and adherence**
- (4) Evaluate the proportion of pregnant and breastfeeding women on PrEP (and not on PrEP) who acquire HIV, who transmit HIV to their infant, and who report adverse events**

- 2. Evaluate patient and provider-level factors associated with the PrEP cascade using quantitative and qualitative approaches (including in-depth interviews)**
- 3. Apply an established mathematical model to simulate the impact of improvement in the PrEP cascade on HIV infections averted (maternal and perinatal)**
- 4. Evaluate the effect of PrEP on vaginal microbiome in pregnant women and the consequent relationship to adverse pregnancy outcomes.**

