##### Inclusion Criteria:

- 1.  $\geq 16$  years old**
- 2. confirmed HIV-negative (confirmed with a 4th generation antigen HIV test)**,
- 3. Intend on giving birth in the MOU facility**
- 4. confirmed to be pregnant**
- 5. without psychiatric or medical contraindications to PrEP.**

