**Step 5: Screening and study consent process:** If the client agrees to participate in the study (*she does not have to agree to take PrEP*), she will be referred to the study recruiter on site where the study counselor will review the **screening consent form** to evaluate study eligibility (see study inclusion, exclusion criteria). Following affirmative answers on the screening consent form the counselor will conduct a rapid HIV test, to test for acute HIV infection using an antigen/antibody test, and a Hepatitis B surface antigen test. Women who test positive for HIV (antigen, antibody or both) and/or Hepatitis B are ineligible for the study and will be referred to the clinic nurse for treatment and care.

All participants who are eligible for the study and agree to participate in the study will receive the study consent form and listen to/watch the consent form on a previously recorded video in Xhosa to ensure that she understands the study design and consent form before signing, asking questions to ensure comprehension.

**Hepatitis B infection (all women at screening):** The blood draw will also be used to test for active Hepatitis B infection using Hepatitis B surface antigen (HBsAg). Women who test HBsAg+ will be excluded from the study and referred for care according to national protocol

- **In addition, we will draw 1ml of serum to be frozen for testing in the case of discrepant results between the Determine HBsAg+ and NHLS laboratory results.**

**Infant consent form:** The participant will review and sign the infant consent form when she returns for her first post-partum visit with her infant.

**Step 6:** Participants will self-collect two vaginal swabs for storage: (1) for laboratory STI testing and (2) for vaginal microbiome analysis. Results for STI testing will be provided in 2-3 weeks after analysis and participants will be called in with STI+ results for treatment and partner referrals

**Step 7:** All participants will complete the baseline survey, which may take approximately 30-45 minutes to complete.

**Step 8:** The participant will receive individual counseling about HIV prevention in pregnancy including PrEP. Risk reduction counseling will be provided for all women and will include:

- **Consistent and correct use of condoms**
- **Knowing your status and partner's status**
- **If partner is HIV infected, should be on ART and achieve viral suppression**
- **Use of drugs and alcohol increases risk of HIV**

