We will also describe the frequency of HIV outcomes, including maternal HIV acquisition and MTCT, and any laboratory or self-reported side effects (e.g. changes in creatinine or self-reported side-effects [GI symptoms, headache, and etc.]). Analyses will include pure-count and person-time approaches; for the latter, confidence intervals will be calculated following the method of Breslow and Day [86]. We will also describe infant outcomes over time (including birthweight, gestational age at delivery, pregnancy loss and any infant illness, hospitalization or death). While we expect the frequency of adverse HIV-related outcomes to be low, we will describe characteristics of women who did/did not acquire HIV, and consider further analyses using the approaches outlined above.

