- g. **Infant measures.** We will collect infant HIV outcomes and birth outcomes from the infant road to health card, and will collect infant growth outcomes at each quarterly visit.

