**Table 1. Study measures for PrEP-PP for AIM 1**

Primary Outcomes	Measurement	Source	Frequency
PrEP initiation	# of women who initiate PrEP over time / total # of women in active cohort = proportion of women who initiate PrEP	Electronic provider log (REDCap)	Quarterly
PrEP continuation	# of women on PrEP who return for study visits (do not miss more than 1 visit) / total # of women in active cohort who are prescribed PrEP= proportion of women on PrEP who continue in PrEP study	Electronic provider log (REDCap)	Quarterly
PrEP persistence (subjective)	# of women reporting taking PrEP in $\geq 5$ out of last 7 days or $\geq 25$ out of last 30 days (self-reported)/ total woman-time on PrEP in active cohort = PrEP persistence rate (subjective)	Electronic provider log (REDCap)	Quarterly
PrEP persistence (objective)	# of women taking PrEP who have $\geq 600$ fmol/punch (~7 doses/week) from DBS TDF-DP at 3rd trimester, delivery, and 6 weeks postpartum (and during sexual risk periods during that time) / total woman-time on PrEP in active cohort = PrEP persistence rate (objective)	Lab analysis of TDF-DP measures	Yearly and end of study
Secondary Outcomes			
Prevention effective persistence	4. # of women reporting adherence to PrEP (as per PrEP persistence subjective measure)/ total woman-time reporting sexual activity in past 30 days	Electronic provider log (REDCap)	Quarterly
	5. # of women having TDF-DP in DBS (as per PrEP persistence objective measure)/ total woman-time reporting sexual activity in past 30 days	Lab analysis of TDF-DP measures	Yearly and end of study

Prevention effective continuation	# of women who don't miss any PrEP study visits/ total woman time reporting sexual activity in prior visit	Electronic provider log (REDCap)	Quarterly
Predictors of attrition at key steps in the PrEP cascade	Individual, pill/study and disease specific predictors of PrEP initiation, continuation and persistence	Study CRFs and in-depth interviews (month 7 and12) (mixed methods)	End of study
Healthcare provider attitudes and knowledge about PrEP in pregnancy	Provider knowledge about PrEP and barriers/facilitators to PrEP prescription in ante and postnatal care	In-depth interviews	Year 1 of study
HIV outcomes	HIV testing data: HIV-uninfected, HIV incidence in mother and child (if mother seroconverts) compared by PrEP use/non-use	Electronic provider log (REDCap)	End of study

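### Follow-up ends at maternal seroconversion, and nothing secures the infant HIV result afterwards in the only mother-infant pairs that can contribute to the MTCT objective

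*Combined protocol and SAP*

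**What the plan says.** **What is to be measured.** Protocol section 2, objective 1(4), asks for the proportion of women "who acquire HIV, who transmit HIV to their infant, and who report adverse events". Protocol section 6 adds: "We will also describe the frequency of HIV outcomes, including maternal HIV acquisition and MTCT". Protocol Table 2 lists child HIV status, when the mother seroconverts, as a secondary outcome. The matching SAP Table 1 entry is "HIV incidence in mother and child (if mother seroconverts) compared by PrEP use/non-use".

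**When follow-up stops.** Protocol section 4 follows women to 12 months postpartum or until they are censored. Its list of censoring events begins with seroconversion, alongside moving away, transfer out of care and loss to follow-up. Protocol section 5, under laboratory tests in all women, repeats the rule: "Seroconverted women will be censored from the remainder of the study". It then provides for the study team to follow seroconverters to see whether viral suppression is reached within 6 months of starting ART.

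**How infant data are to be obtained.** Protocol section 5, Step 5: "The participant will review and sign the infant consent form when she returns for her first post-partum visit with her infant". SAP Study measures, item g: "We will collect infant HIV outcomes and birth outcomes from the infant road to health card". The protocol's Sources of data also lists abstraction from routine care records.

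**Who is analysed.** Protocol section 6, the SAP sample-size section and SAP section 2.4 all base the analysis on women who complete 12 months postpartum.

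**The concern.** The event that makes an infant eligible for the MTCT outcome is the same event that ends the mother's participation. Censoring the PrEP cascade at seroconversion is sensible, because a woman with HIV is no longer a candidate for PrEP. Ending participation altogether is a different matter, since the transmission question only opens at that point.

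At stake is a stated objective. A report of few or no transmissions could reflect when observation stopped rather than what happened to the infants. Birth outcomes of women infected during pregnancy face the same problem, since they too occur after the mother has been censored.

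**Working it through.** The documents give no expected count, power or precision for MTCT, so there is no figure to reproduce. The check sets the provisions side by side.

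1. **Who can contribute an event.** Inclusion requires a negative HIV status, "confirmed with a 4th generation antigen HIV test". An MTCT event therefore needs maternal seroconversion on study, and both outcome tables are worded that way.

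2. **What censoring means here.** Section 4 treats it as the end of follow-up. The list groups seroconversion with losses from the study. The laboratory section extends it to the rest of the study. The monthly report template in SAP section 4 counts censored participants under withdrawals. Together these point to the end of participation, not only of the cascade analysis. The SAP's own seroconversion paragraph leaves out the censoring sentence but does not revoke it.

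3. **What happens to each pair, read literally.**
   - *Seroconversion in pregnancy:* the mother is censored before delivery, so before the postpartum visit at which infant consent is signed. Mean follow-up is 18 months, of which 12 are postpartum, leaving 18 − 12 = 6 months antenatal. If risk were constant and attrition small (both assumptions), about 6/18, or one third, of seroconversions would fall here.
   - *Seroconversion after delivery:* infant consent may already be held, but the mother leaves at the visit that detects her infection. An infant infection found by then is counted. No provision covers one found later.

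4. **Whether another source closes the gap.** The Road to Health card is named, but not how it is obtained once study visits stop. Both outcome tables give the electronic provider log as the source for child HIV, and the protocol table sets the frequency at every visit. Routine-record abstraction is listed without mention of infant HIV results, duration or consent. The follow-up of seroconverters concerns maternal suppression and does not mention the infant.

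5. **Whether the analysis can repair it.** The completer restriction would exclude these pairs even if records were found. The SAP's inverse-probability-of-censoring weighting and multiple imputation do not help. If every pair with an infected mother is censored by rule, no uncensored pair of that kind remains to be weighted up or to inform the imputation.

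6. **Direction of error.** Let n be the infants of seroconverting mothers, d1 the infections found by the censoring visit and d2 those found later. If unknown results are treated as negative, the estimate is d1/n instead of (d1 + d2)/n, too low by d2/n. If unknown results are excluded, the estimate rests on whichever infants happen to have records, and its direction is not determined. The documents do not say which applies, so underestimation is probable but not certain.

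7. **Number affected.** Planned person-time is at most about 1200 × 1.5 = 1800 person-years. A count would also need the incidence in this cohort, the transmission risk given the planned care, and the split of infant infections before and after maternal detection. The plan's incidence of 10.7 per 100 person-years is an upper background figure, its 30% transmission applies to acute maternal infection, and no split is given. I therefore give no count.

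**The case against.** The strongest reply is that the plan clearly means to obtain these results. Both outcome tables name the child's HIV status in exactly this group. The card and routine records need not depend on an attended study visit. The data-management section keeps folder numbers until routine data are linked. The study team stays in contact with seroconverters, and both documents provide for an infant who seroconverts at any point in the study. On this view, censoring ends only the cascade and maternal-incidence follow-up.

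Much of this stands. A reader might infer that infant HIV will simply go unobserved in these pairs; the documents do not support that, because the intention and possible sources are written down. What does not stand is that the intention is secured. No section says that infant ascertainment continues after the mother is censored, for how long, or under which consent.

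Three further inferences should be resisted:
- **The Aim 3 model loses its vertical-transmission input.** The modelling section takes cascade results from the cohort and simulates vertical risk by a previously described method. It speaks of using cohort outcomes to parameterise and validate the model but names no cohort MTCT input.
- **Birth outcomes after seroconversion in pregnancy are lost.** Women must intend to deliver at the study facility, and the card and routine records could supply these outcomes. They are at risk, not lost.
- **Consent is absent.** The consent forms were not available for this review, so the maternal form may already permit record linkage.

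**Conclusion.** The point holds as an unresolved conflict between the censoring rule and a stated objective, with no specified route to the infant outcome after the mother's censoring date. On a literal reading, MTCT would be incomplete and probably underestimated. The direction depends on how unknown infant results are handled, which the plan leaves open. The conflict applies to every at-risk pair, but the number cannot be derived from the documents.

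This should be corrected, but it is not a critical defect. Infant HIV is a secondary, descriptive outcome. The primary outcomes are the cascade proportions, for which censoring at seroconversion is appropriate. The conclusion rests on reading censoring as the end of participation, the more natural reading of the four provisions in step 2. It draws nothing from the protocol's visit schedule, which is incomplete in the copy reviewed.

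**What to change.** Reconcile protocol section 4 (follow-up and the censoring list), section 5 (infant consent in Step 5 and the seroconversion paragraph), the section 6 analysis set and Table 2 with the SAP (sample-size section, section 2.4, Study measures item g and Table 1):

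- Censor only the PrEP cascade and maternal-incidence outcomes at seroconversion.
- Keep the mother-infant pair in outcome ascertainment to 12 months postpartum for infant HIV and birth outcomes, through existing visits or the routine-record abstraction already planned. Name the source.
- Obtain infant or record-linkage consent at or before seroconversion where it is not already held.
- Define the MTCT denominator as all infants of seroconverting mothers, report how many have unknown HIV status, and do not count unknown as negative.
- Exempt these infant outcomes from the 12-month-completer restriction.

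The cost is amended wording, record abstraction and a consent step for a limited number of pairs. No extra enrolment is needed, and the primary cascade analyses do not change.
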